To test the effectiveness of short BBT-I program for chronic insomnia in comparison with zopiclone in Russian population.

Secondary Objectives

Identification of anthropometric, psychological and polysomnographic predictors of effectiveness of each method.

STUDY DESIGN

Study Overview

Prospective randomized crossover study. In accordance with this design every patient will receive two different treatment courses in random sequence: zopiclone or structured educational program (BBT-I) delivered in two sessions. Patients of the zopiclone-first group will receive the medication therapy for the first two weeks followed by educational program. Patients of the BBT-I-first group will receive two-week educational program followed by medication therapy.

Each treatment course will be separated by 2-weeks washout period that will provide the opportunity to evaluate the sustainability of treatment effect.

The total duration of the study will be 8 weeks with 6 visits including 1 night polysomnography (PSG), 2 face-to-face structured educational program sessions and 5 diagnostic interviews. Total duration of the study will be 2 years.

Criteria for evaluation

Primary Efficacy Endpoint

Proposed primary efficacy endpoint is change of insomnia severity index (ISI) after treatment. Criterion of response to the treatment will be defined as the reduction of ISI score reduction of >7 points from baseline. This criterion is indicative of moderate improvement and validated as clinically significant (Morin, Belleville & Belanger, 2011). Remission criterion will be defined as final

ISI score of 7 points or less. Nonresponse criterion will be defined as ISI score decrease of ≤ 7 points from baseline.

Secondary Efficacy Endpoints

1. Insomnia severity index self reported insomnia symptoms severity . Each item is scored 0 (no problem) - 4 (very big problem) with total between 0-28 (absence of insomnia (0-7); sub-threshold insomnia (8-14); moderate insomnia (15-21); and severe insomnia (22-28).
2. Beck Depression Inventory. 21-item questionnaire assessing (on 4-point Likert scales) the intensity of depressive symptoms in the past week
3. State-trait anxiety inventory. 2-part questionnaire assessing state (situational) and trait anxiety. Both situational and trait parts comprise 20 items rated on a 4-point Likert scale.
4. Dysfunctional beliefs about sleep scale. questionnaire assessing sleep related cognitions in 16 item rated on a 10-point Likert scale.

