All concomitant medication and concurrent therapies will be documented at baseline examination and at visit days. Dose, route, unit frequency of administration, and indication for administration and dates of medication will be captured.

Demographics

Demographic information (date of birth, gender) will be recorded at baseline examination.

Medical History

Relevant medical history, including history of current disease, other insomnia history, and information regarding underlying diseases will be recorded at baseline examination.

Physical Examination

A complete physical and neurological examination will be performed by the investigator who is a neurologist at baseline examination.

Vital Signs

Body temperature, blood pressure, pulse will be measured after resting for 5 minutes at baseline examination.

Polysomnography

1-night in-lab PSG (without adaptation night) will be performed at baseline examination. Standard polysomnography montage includes 6 monopolar electroencephalography (EEG) channels Fp₁A₂, Fp₂A₁, C₃A₂, C₄A₁, O₁A₂, O₂A₁; 1 submental electromyogram (EMG) channel; 2 electrooculogram (EOG) channels; 2 EMG channels of the right and left tibialis anterior muscles; 1 electrocardiogram channel; oronasal airflow pressure; thoracic and abdominal efforts; respiratory sound; oxygen saturation; body position with videomonitoring

Questionnaire

Subjects will be asked to fill in self-report questionnaires: Beck Depression Inventory (BDI), State-trait anxiety inventory (STAI), Toronto Alexithymia Scale – short version TAS-20, Big Five Questionnaire (BFQ-2R), Pittsburg Sleep Quality Index (PSQI), Insomnia Severity Index (ISI), Dysfunctional beliefs about sleep scale (DBAS), Sleep hygiene index (SHI) at baseline examination.

During the next 4 visits participants will repeatedly undergo diagnostic tests including BDI, STAI, PSQI, ISI, DBAS, SHI.

Adverse Events

Information regarding occurrence of adverse events will be captured throughout the study. Duration (start and stop dates and times), severity, outcome, treatment and relation to study drug will be recorded on the case report form (CRF).

Clinical Laboratory Measurements

β -adrenoreactivity test

Peripheral blood sample will be collected in a sterile tube and tested in lab for erythrocyte membranes β -adrenoreactivity by a method based on detection of adrenoreceptor sensitivity to-endogenous catecholamines

EVALUATIONS BY VISIT

Visit 1 (Day 1/Week 1/ Month 1)

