Subjects withdrawn from the study treatment will be replaced. Subjects withdrawn from the study after Visit 5 but prior to Visit 6 won't be replaced.

Protocol Violations

Protocol violations for this study include, but are not limited to, the following:

- Failure to meet inclusion/exclusion criteria

- Use of a prohibited concomitant medication
- Non-compliance with study drug regimen, and questionnaires completion

Failure to comply with Good Clinical Practice (GCP) guidelines will also result in a protocol violation. If a protocol violation occurs, a Protocol Violation Form detailing the violation will be generated.

DATA SAFETY MONITORING

There will be no data monitoring committee

STATISTICAL METHODS AND CONSIDERATIONS

A Statistical Analysis Plan (SAP) is written describing all analyses that will be performed.

Data Sets Analyzed

All subjects matching inclusion and exclusion criteria who will complete at least one treatment course (BBT-I or medication) and fill in questionnaires prior and after the treatment will be included in the safety analysis.

Demographic and Baseline Characteristics

The following demographic variables at screening will be summarized by dose level: gender, age, height and weight. Continuous variables will be presented in means and standard deviation ($M \pm SD$).

Analysis of Primary Endpoint

Statistical significance of differences between ISI level before and after treatment for both treatment methods will be evaluated with Student's t-test after confirmation of normal variable distribution by Kolmogorov-Smirnov test. For continuous variables with distribution other than normal Mann-Whitney U-test will be used. For comparison of the proportions Pearson chi-squared test will be performed.

Criterion of response to the treatment is defined as the reduction of ISI score reduction of >7 points from baseline. This criterion is indicative of moderate improvement and validated as clinically significant (Morin, Belleville & Belanger, 2011). As well the criterion corresponds to approximately 1 standard deviation of the pretreatment values (Cohen effect size of approximately 1.0). Remission criterion is defined as final ISI score of 7 points or less. Nonresponse criterion is defined as ISI score decrease of ≤ 7 points from baseline.

Analysis of Secondary Endpoints

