Statistical significance of differences between BDI, STAI, PSQI, DBAS, SHI, β -adrenoreactivity level, sleep diary data before and after treatment for both treatment methods will be evaluated with Student's t-test after confirmation of normal variable distribution by Kolmogorov-Smirnov test. For continuous variables with distribution

other than normal Mann-Whitney U-test will be used. For comparison of the proportions Pearson chi-squared test will be performed.

Based on the response criterion participants will be divided into two groups: responders and nonresponders for each method of treatment. Comparison of responders and nonresponders baseline quantitative characteristics (polysomnographic, antropometric, psychometric) will be performed using Student's t-test (for normal data distribution) or Mann-Whitney U-test (for abnormal data distribution). Statistical significance will be set at a p-value less 0,05.

Safety and tolerability data will be summarized by treatment group. Adverse events will be tabulated by treatment group and include the number of patients for whom the event occurred, the rate of occurrence, and the severity and relationship to study drug.

Interim Analysis

Interim statistical analysis will be performed after 20 patients complete the study protocol.

Sample Size and Randomization

The number of subjects planned to be enrolled is 40. This is a representative sample for study of treatment effects. The crossover design of the study will allow us to compare two therapeutic approaches with a relatively small sample size and to determine the predictors of effectiveness for each treatment.

DATA COLLECTION, RETENTION AND MONITORING

Data Collection Instruments

The Investigator will prepare and maintain adequate and accurate source documents designed to record all observations and other pertinent data for each study subject. The information corresponding to each visit will be entered to the study database and to paper CRF.

The Investigator is responsible for all information collected on subjects enrolled in this study. All data collected during the course of this study will be reviewed and verified for completeness and accuracy by the Investigator.

Data Management Procedures

The data will be entered into a validated database. The Investigator is responsible for data processing, in accordance with procedural documentation.

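### The unadjusted responder comparison is biased towards naming baseline ISI a predictor of response, because response is itself calculated from baseline ISI

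*Combined protocol and SAP*

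**What the plan says.** Under Secondary Objectives, the plan's aim is: "Identification of anthropometric, psychological and polysomnographic predictors of effectiveness of each method". Analysis of Primary Endpoint defines the grouping: "Criterion of response to the treatment is defined as the reduction of ISI score reduction of >7 points from baseline", with nonresponse as a drop of 7 points or less. Analysis of Secondary Endpoints splits participants by this criterion for each treatment and adds: "Comparison of responders and nonresponders baseline quantitative characteristics (polysomnographic, antropometric, psychometric) will be performed using Student's t-test", with Mann-Whitney where data are not normal. The threshold is: "Statistical significance will be set at a p-value less 0,05". The matching sentence in the synopsis (Statistics, Primary Analysis Plan) refers to baseline quantitative characteristics without any limit.

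The Questionnaire section under Clinical Assessments lists among the Visit 1 instruments: "Pittsburg Sleep Quality Index (PSQI), Insomnia Severity Index (ISI), Dysfunctional beliefs about sleep scale (DBAS), Sleep hygiene index (SHI) at baseline examination". No section excludes ISI from the predictor comparison, adjusts for it, or mentions regression to the mean. A remission criterion based on the final score alone is defined, but the responder split does not use it.

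**The concern.** The t-test asks whether responders and nonresponders have the same mean baseline value. For baseline ISI that null hypothesis fails for a reason unrelated to treatment. Response is (baseline ISI − final ISI) > 7, so a patient whose Visit 1 score is high through a bad week or measurement error tends to score lower later and be counted as a responder. Baseline ISI is then higher in responders even if true benefit does not depend on severity.

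Predictors are the only secondary objective, and the Study Rationale ties them to choosing treatment for the individual patient. A finding that more severe insomnia responds better would be read as guidance on whom to treat, when part or all of it could come from how response is computed.

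**Working it through.** **Inputs from the documents.** Sample size (Sample Size and Randomization): "The number of subjects planned to be enrolled is 40", each receiving both treatments. Response: ISI drop >7. ISI range: 0–28. Level: 0.05, taken as two-sided because the plan does not say. Baseline SD: not stated directly, but Analysis of Primary Endpoint equates the criterion with about 1 SD of pretreatment values, so SD ≈ 7 / 1.0 = 7. No minimum ISI is set for entry. The plan gives no power or error-rate figure for this comparison, so there is nothing to reproduce.

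**Assumed, not in the documents.** Mean baseline ISI 18; mean true drop 7.5 with SD 4, independent of true severity (about half respond); ISI reliability 0.7 to 0.9; SD 4.5 as a cautious alternative to 7.

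**Algebra.** Let baseline = T + e1 and final = T − d + e2, with d independent of T, e1 and e2. Then

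corr(baseline, drop) = error variance / (SD of baseline × SD of drop),

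which is positive whenever reliability is below 1. At reliability 0.8:

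- SD 4.5: error variance = 0.2 × 20.25 = 4.05; SD of drop = √(16 + 2 × 4.05) = 4.91; correlation = 4.05 / (4.5 × 4.91) = 0.18.
- SD 7: error variance = 0.2 × 49 = 9.8; SD of drop = √(16 + 2 × 9.8) = 5.97; correlation = 9.8 / (7 × 5.97) = 0.23.

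**Simulation of the planned test.** 40 patients, scores rounded and limited to 0–28, no relation between benefit and severity. Rejection rate for baseline ISI at nominal 5%:

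| Assumed reliability | SD 4.5 | SD about 7 | SD 4.5, entry at ISI 15 or more |
|---|---|---|---|
| 0.9 | about 9% | about 16% | about 6% |
| 0.8 | about 16% | about 27% | about 10% |
| 0.7 | about 26% | about 40% | about 14% |

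At SD 7 without the 0–28 limits, and with the SD of true change between 3 and 5, the rates are 9–12%, 18–26% and 29–41%. Some of the excess in the SD 7 column, most visibly at reliability 0.9, is therefore the floor of the scale (a baseline of 7 or less cannot drop by more than 7). The last column shows that the coupling remains when low scorers are excluded.

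**Control.** A characteristic unrelated to ISI is rejected in 5.2% of runs by t-test and 5.0% by Mann-Whitney. The inflation comes from the coupling, not from the test.

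**Which baseline.** If second-course response is counted from Visit 3 and the characteristic is taken at Visit 1, the errors are separate and the rate is 4.4–5.2%.

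**Other questionnaires from the same visit** (SD 4.5, true-score correlation 0.6 with ISI). With error correlation 0 to ISI there is no inflation (4–5%). With error correlation 0.5–0.8 the rate is about 7–12% at reliability 0.8 and 9–18% at 0.7.

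**The case against.** The strongest reply is that baseline ISI is only inferred to be a tested predictor. The word psychometric is not itemised, the objective speaks of psychological predictors, and ISI is the primary endpoint. This stands as a limit on certainty. But the Questionnaire section lists ISI with the other baseline scales and the synopsis wording has no restriction, so the inference is reasonable.

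A second reply is that the inflation may be modest: 6–9% at reliability 0.9 with SD 4.5. That also stands. The size depends on a reliability that the documents do not give.

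A third is that the coupling may be absent from second courses. The documents mostly use baseline for Visit 1, which would carry the coupling into both courses, but they do not settle the point. If second-course response is counted from Visit 3 against a Visit 1 characteristic, only first courses are affected and the inflation for each treatment is diluted.

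Two stronger readings are tempting. A reader might infer that the test will find severity to be a predictor when it is not one. In the scenarios tabulated no rate reaches a majority. Rates of 50–99% appear only if pre- and post-treatment SDs are equal and the scores correlate between 0.7 and 0; baseline is then genuinely related to change through regression to the mean, so these are not false-positive rates under the strict null. A reader might also infer that every questionnaire from Visit 1 is contaminated. That needs errors correlated with those of ISI, for which the documents give no figure.

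**Conclusion.** The point holds as a bias with an inflated error rate, not as a certain false finding. For baseline ISI, the planned comparison exceeds its nominal 5% even when benefit is unrelated to severity: about 9–26% at SD 4.5 and 16–40% at the implied SD of about 7, for reliability 0.9 down to 0.7, or about 6–14% if all entrants had ISI 15 or more (SD 4.5). Nothing in the plan removes it. It applies to first courses, and to second courses if their baseline is Visit 1. It concerns the predictor objective only; the primary treatment comparison is untouched. The figures rest on assumed reliability, mean scores and spread of true change, and on baseline ISI being among the psychometric characteristics. Spillover to other scales is conditional on correlated errors.

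**What to change.** In Analysis of Secondary Endpoints, and in the matching synopsis sentence, exclude baseline ISI from the characteristics tested against response. Report its mean in responders and nonresponders descriptively, stating that the two are linked by construction.

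As an optional sensitivity check for the other questionnaires completed at the same visit (PSQI, BDI, STAI, DBAS and SHI), also regress end-of-course ISI on the characteristic with pre-course ISI as covariate. If TAS-20 and the Big Five are left out, give the reason. Call a predictor supported only if both analyses are significant and point in the same direction of benefit: higher in responders with a negative coefficient on final ISI, or lower in responders with a positive one. The wording matters: lower final ISI is better, so a rule asking for the same algebraic sign would reject true predictors.

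In simulation the joint rule kept false positives at about 1–4% at a true-score correlation of 0.6 with ISI, but gave about 7% in one case at 0.2 (reliability 0.7, error correlation 0.8). It should not be described as controlling error in every scenario.

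No new data are needed, since ISI is already repeated at later visits. The main change costs only the p-value for baseline severity, which cannot be interpreted as planned. The optional check adds one regression per questionnaire and loses power, in one simulated case from 79% to 59%, partly because the unadjusted figure includes the artefact.

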APPENDIX 1. SCHEDULE OF STUDY VISITS

	VISIT 1 (Day1/Week1/Month 1)^a	VISIT 2 (Day14/Week2 /Month 1)^a	VISIT 3 (Day28/Week4 /Month 1)^a	VISIT 4 (Day42/Week6 /Month 2)^a	VISIT 5 (Day56/Week8 /Month 2)
Informed Consent	X				
Medical History	X				
Complete Physical and neurological Exam	X				
Abbreviated Physical Exam		X	X	X	X
Height	X				
Weight	X				
Vital Signs	X				
Polysomnography	X				
β-adrenoreactivity test	X	X	X	X	X
BDI, STAI, PSQI, DBAS, SHI	X	X	X	X	X
Big five questionnaire, TAS-20	X				
Randomization	X				
Administration of Study Drug	X		X		
BBT-I ^b	X		X		
Initiate Subject Diary	X				
Subject Diary Review		X	X	X	X
Adverse Experiences		X	X	X	X

^a ±2 day

^b BBT-I was delivered in two weekly sessions, so during BBT-I phase each subject had additional (1.2 or 3.2) visit for BBT-I session

Study design
